### 9.1.2 List of Graphs

- Boxplots of background-adjusted IFN- $\gamma$  and/or IL-2 response magnitude by T-cell subset, HIV protein, visit, and group/treatment arm using Fisher exact test and/or MIMOSA criteria. [*State layout – this depends on the comparisons of interest. The default is treatment groups side by side per protein, one T-cell subset and one visit per graph.*]

- [*If marginal cytokine data available*] Boxplots of background-adjusted marginal cytokine response magnitude by T-cell subset, HIV protein, visit, and group/treatment arm using Fisher exact test and/or MIMOSA criteria. State the default layout or other desirable layout: e.g., treatment groups side by side per protein, one T-cell subset and one visit per graph.
- [*If polyfunctional graphs requested*] Boxplots of cytokine degree by T-cell subset, HIV protein, visit, and group/treatment arm. State the default layout or other desirable layout: e.g., treatment group side by side, one T-cell subset, visit, protein per graph.
- [*If polyfunctional graphs requested*] Boxplots for each cytokine combination of a given degree by T-cell subset, HIV protein, visit, and group/treatment arm. State the default layout or other desirable layout: e.g., treatment group side by side, one T-cell subset, visit, protein per graph.
- [*State other pre-specified analyses (delete if none)*]

## 9.2 Neutralizing Antibody

Neutralizing antibodies against HIV-1 were measured as a function of reductions in Tat-regulated luciferase (Luc) reporter gene expression in TZM-bl cells [2, 3].

- Vaccine strains: CH505TF (Tier 2), CH505.w4.3 (Tier 1A)

Tier	Subtype	Vaccine strain	Isolate
2	C	Yes	CH505TF
1A	C	Yes	CH505.w4.3

Specimens from other time points may also be analyzed at the discretion of the HVTN Laboratory Program, which may be contingent on the results of the primary immunogenicity time point. Those time points may include visit 2 (day 0) and/or visit 9 (day 364 - 6 months post final vaccination).

Data from blood draw dates outside the allowable visit window and assay results deemed unreliable for analysis by the lab were excluded from the analysis. Post-infection samples from HIV-infected participants are excluded.

Response to a virus/isolate was considered positive if the neutralization titer was above a pre-specified cutoff. A titer was defined as the serum dilution that reduced relative luminescence units (RLUs) by 50% and 80% relative to the RLUs in virus control wells (cells + virus only) after subtraction of background RLU (cells only). The prespecified cutoff for ID50 and ID80 was 10. Tables show the response rates to each virus/isolate and corresponding 95% confidence intervals calculated by the score test method [1].

Barnard's test was used to compare response rates between treatment groups, while the Wilcoxon rank sum test was used to compare response magnitudes between treatment groups, among positive and negative responders, and among the subset of positive responders. Response

magnitude comparisons among positive responders will not be done if there are fewer than 5 responders per treatment group.

Plots of neutralizing antibody titers show both response rates and the distribution of magnitude. Positive responses are indicated by dots color-coded by treatment group, and negative responses by gray triangles. Data points for each participant are connected by a gray line. The mid-line of the box denotes the median and the ends of the box denote the 25th and 75th percentiles. The whiskers that extend from the top and bottom of the box extend to the most extreme data points that are no more than 1.5 times the interquartile range (i.e., height of the box) or if no value meets this criterion, to the data extremes.

### 9.2.1 List of Tables

- Response rate table by lab, cell type, virus, inhibitory dilution (ID50/ID80), visit, day, and group/treatment arm. [State positivity criteria in footnote.]
- Summary statistics (i.e., min, mean, median, max) among responders by lab, cell type, virus, inhibitory dilution (ID50/ID80), visit, day, and group/treatment arm.
- Summary statistics (i.e., min, mean, median, max) among all participants (positive and negative responders) by lab, cell type, virus, inhibitory dilution (ID50/ID80), visit, day, and group/treatment arm.
- Response rate comparison of T1 vs. T2, by visit, using Barnard's test.
- Response magnitude (ID50 & ID80 titer) comparison between T1 and T2 for vaccine strains by visit among all participants, using Wilcoxon rank sum test.
- Response magnitude (ID50 & ID80 titer) comparison between T1 and T2 for vaccine strains by visit among positive responders, using Wilcoxon rank sum test. (if there are more than 5 responders per treatment group).

### 9.2.2 List of Graphs

- Bar and boxplots of response rate and neutralizing antibody titers by virus, inhibitory dilution (ID50/ID80), visit day, and group/treatment arm.
- Bar and line plots (spaghetti plots) of response rate and neutralizing antibody titers by virus, inhibitory dilution (ID50/ID80), and group/treatment arm.

### 9.3 Binding Antibody Multiplex Assay

Serum HIV-1-specific IgG responses at a 1:50 starting dilution followed by a 5-fold serial dilution for a total of six dilution points if titrations are warranted against CH505TF gp120 (transient transfection) and CH505TF gp120 (stable transfection) or CH505TF\_D8gp120/293F at visits 2 (M0, baseline) and 7 (M6.5, 2 weeks post 3rd vaccination) were measured on a Bio-Plex instrument (Bio-Rad) using a standardized custom HIV-1 Luminex assay [5, 6, 7]. The readout was background-subtracted mean fluorescence intensity (MFI), where background referred to two plate level controls (i.e., two blank wells run on each plate). Standard positive and negative controls were included in each assay to ensure specificity and for maintaining consistency and reproducibility between assays. The positive control includes purified polyclonal IgG from HIV subjects (HIVIG). The negative control was NHS (HIV-1 sero-negative human sera) and blank beads.

Several criteria were used to determine if data from an assay were acceptable and could be statistically analyzed. First, the blood draw date must have been within the allowable visit window as determined by the protocol. Post-infection samples from HIV-infected participants are excluded. Second, if the blank bead negative control exceeded 5,000 MFI, the sample was repeated. If the repeat value exceeded 5,000 MFI, the sample was excluded from analysis due to high background. The preset assay criteria for sample reporting were: coefficient of variation (CV) per duplicate values for each sample are  $< 20\% \geq 50$  beads counted per antigen. To control for protein performance, the preset criteria include that the positive control titration in each assay must be within  $\pm 3$  standard deviations of the mean for each antigen (tracked with a Levey-Jennings plot for high MFI and Area Under the Curve (AUC)).

Panel	Isolate	Clade
-	CH505TF gp120 (transient transfection)	C
-	CH505TF gp120 (stable transfection)	C

Samples from post-enrollment visits were declared to have positive responses if they met three conditions: (1) the MFI minus Blank values were  $\geq$  antigen-specific cutoff at the 1:50 dilution level for IgG (based on the 95th percentile of baseline samples as calculated by SAS PROC UNIVARIATE default method, and at least 100 MFI minus Blank), (2) the MFI minus Blank values were greater than 3 times the baseline (day 0) MFI minus Blank values, and (3) the MFI values were greater than 3 times the baseline MFI values.

Net MFI (MFI minus Blank) were truncated at 22,000, the upper limit of the linear range of the assay. Additionally, samples were excluded from threshold calculation and analysis if the baseline analyte net MFI exceeded 6500. For each combination of individual and antigen the area under the titration curve (AUC) at each time point was calculated over dilutions [insert dilution factors of the titration series] using the trapezoidal integration, with base 10 log-transformation of the dilutions and with truncation at zero in the case of negative net MFI values and no ceiling (at 22,000) truncation.

Tables show positive response rates and corresponding 95% confidence intervals calculated by the Wilson score method [1], as well as summary statistics among positive responders and all participants.

Barnard's test was used to compare response rates between treatment groups, while the Wilcoxon rank sum test was used to compare response magnitudes between treatment groups, among positive and negative responders, and among the subset of positive responders. Response magnitude comparisons among positive responders will not be done if there are fewer than 5 responders per treatment group.

Net MFI responses at the 1:50 dilution level and the titers (AUC) were used to summarize the magnitude at a given time-point. These distributions are displayed graphically by treatment arm. Plots include data from responders in color and non-responders in gray, with box plots based on

data from responders superimposed on the distribution. Data points for each participant are connected by a gray line. The mid-line of the box denotes the median and the ends of the box denote the 25th and 75th percentiles. The whiskers that extend from the top and bottom of the box extend to the most extreme data points that are no more than 1.5 times the interquartile range (i.e., height of the box) or if no value meets this criterion, to the data extremes.

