### 6.1.2 Sample size calculations for immunogenicity

Binding antibodies will be measured by geometric mean fluorescence intensity (FI) for homologous proteins. We will test the null hypothesis that the geometric mean FI in the transient arm is less than 1/4 of the geometric mean FI in the stable arm. The power to reject this null hypothesis depends on the variability of the binding antibodies measurements and sample sizes. Based on HVTN 505 data, the standard deviation of the natural log of geometric mean FI at the dilutions optimized for immune correlates analyses, which maximize the proportion of samples within the linear range of the dilution-response curve, is around 1.4. Table 6-3 lists the power under a range of standard deviations, non-inferiority margins, and sample sizes.

The power study assumes that  $\log_e$ (geometric mean FI for a panel of Envs) is normally distributed and has the same spread in both arms. We will form a 95% confidence interval for the difference in  $\log_e$ (FI)s between the transient arm and the stable arm and compare the lower confidence interval to  $\log_e(1/4)$ . Under the parameters of the proposed study, the estimated power to reject the null hypothesis ranges from 0.86 to 0.63 for standard deviation ranging from 1.2 to 1.6.

**Table 6-3 Power to reject the null hypothesis that the geometric mean FI in the transient arm is less than non-inferiority margin of the geometric mean FI in the stable arm.** Standard deviation: spread of  $\log_e$ (FI); n: sample size for each arm. The alpha level is set at 0.05 for a two-sided test.

Standard Deviation	Non-inferiority Margin																				
	1/8			1/4			1/2			1/8			1/4			1/2					
	n = 10			n = 15			n = 20			n = 10			n = 15			n = 20					
1.2			0.96		0.69		0.23				1.00		0.86		0.33		1.00		0.95		0.43
1.4			0.88		0.55		0.18				0.98		0.74		0.26		1.00		0.86		0.33
1.6			0.78		0.45		0.15				0.93		0.63		0.21		0.98		0.76		0.27

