#### 6.4.4.3 Analysis of multiplexed immunoassay data

Two approaches will be considered to evaluate the magnitude and breadth of these responses. First, M-B curves maybe employed to display individual- and group-level response breadth as a function of magnitude. Two choices are to compare the M-B curves among vaccine arms, as follows: a non-parametric Wilcoxon rank sum test on the subject-specific area-under-the M-B curve (AUC-MB) or a Kolmogorov-Smirnov type test on the 2 group-average M-B curves. Simulations can be used to obtain 2-sided p-values for the latter test. Second, a weighted-average score-like variable may be constructed to account for the correlations between analytes as an integrate magnitude of responses to multiple analytes. Similar group comparison methods described in the first approach may be adopted. Details of either approach will be described in the SAP.

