## 10.5 Endpoint assays: humoral

### 10.5.1 Binding antibody multiplex assay (BAMA)

HIV-1-specific total binding IgG antibodies to CH505TF gp120 and a panel of heterologous gp120s will be assessed on serum samples from study participants taken at the primary immunogenicity timepoints and baseline. In addition, HIV-1-specific total binding IgA antibodies and binding to IgG subclasses (IgG1, IgG2, IgG3, and IgG4) may also be assessed. Specimens from other timepoints may also be assayed based on the results of the initial assay.

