## **3 OBJECTIVES AND ENDPOINTS**

### **3.1 Primary objectives and endpoints**

*Primary objective 2:*

To evaluate and compare the magnitude of binding antibody responses elicited by the CH505TF gp120 proteins produced via transient and stable transfection methods

*Primary endpoint 2:*

HIV-specific total IgG binding antibody responses against the homologous proteins, as assessed by BAMA at peak timepoint (2 weeks after 3rd vaccination)

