### 9.3.1 List of Tables

- Response rate table by lab, isotype, antigen, visit, day, and group/treatment arm.
- Summary statistics (i.e., min, mean, median, max) of net MFI among all participants (positive and negative responders) by lab, isotype, antigen, visit, day, and group/treatment arm.
- Summary statistics (i.e., min, mean, median, max) of net MFI among responders by lab, isotype, antigen, visit, day, and group/treatment arm.
- Summary statistics (i.e., min, mean, median, max) of AUC among all participants (positive and negative responders) by lab, isotype, antigen, visit, day, and group/treatment arm.
- Summary statistics (i.e., min, mean, median, max) of AUC among responders by lab, isotype, antigen, visit, day, and group/treatment arm.
- Response rate comparison between T1 and T2 at visits 2 (M0, baseline) and 7 (M6.5, 2 weeks post 3rd vaccination), using Barnard's test.
- Net MFI comparison between T1 and T2 at visits 2 (M0, baseline) and 7 (M6.5, 2 weeks post 3rd vaccination) among all participants, using Wilcoxon rank sum test.
- Net MFI comparison between T1 and T2 at visits 2 (M0, baseline) and 7 (M6.5, 2 weeks post 3rd vaccination) among positive responders, using Wilcoxon rank sum test. (if there are more than 5 responders per treatment group).
- AUC comparison between T1 and T2 at visits 2 (M0, baseline) and 7 (M6.5, 2 weeks post 3rd vaccination) among all participants, using Wilcoxon rank sum test.
- AUC comparison between T1 and T2 at visits 2 (M0, baseline) and 7 (M6.5, 2 weeks post 3rd vaccination) among positive responders, using Wilcoxon rank sum test. (if there are more than 5 responders per treatment group).

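### SAP 9.3 does not carry over the protocol's single primary binding variable: no antigen, combination or readout is named primary, and its text and antigen table disagree

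*SAP*

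**What the plan says.** **Endpoint.** Protocol 5.1 and SAP 3.1 give the same primary endpoint 2: "HIV-specific total IgG binding antibody responses against the homologous proteins, as assessed by BAMA at peak timepoint". The proteins are plural and none is singled out.

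**Powered variable.** Protocol 6.1.2 states: "Binding antibodies will be measured by geometric mean fluorescence intensity (FI) for homologous proteins". It sets one null hypothesis (transient-to-stable ratio below 1/4) and one decision: the lower limit of a 95% confidence interval for the difference in log FI, compared with log(1/4). The power assumption concerns the log of the "geometric mean FI for a panel of Envs) is normally distributed and has the same spread in both arms". That panel is not listed, and the section does not make clear whether the geometric mean runs over antigens or over participants.

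**Assay and combination.** Protocol 10.5.1 says that "total binding IgG antibodies to CH505TF gp120 and a panel of heterologous gp120s will be assessed", with CH505TF gp120 in the singular and no production method. Protocol 6.4.4.3 mentions an optional weighted score across analytes and adds: "Details of either approach will be described in the SAP". The SAP contains no such score.

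**SAP 9.3.** The text names "CH505TF gp120 (transient transfection) and CH505TF gp120 (stable transfection) or" the 293F-produced CH505TF protein, with no criterion for the alternative. The antigen table in the same section lists only the transient and stable CHO proteins. Magnitude is summarised by net MFI at 1:50 and by AUC. SAP 9.3.1 lists the "Net MFI comparison between T1 and T2 at visits 2 (M0, baseline) and 7" and the matching AUC comparison, each by Wilcoxon rank sum test, once in all participants and once in positive responders. The summary tables are by antigen; the comparison items do not mention antigen. SAP section 9 adds bootstrap intervals for means or medians, without a margin.

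**The concern.** The protocol planned one question with one answer. The SAP, which should make that operational, replaces it with a set of comparisons of equal standing on other quantities. A reader of the final report could not tell which result answers primary objective 2, and the stated power applies to none of them.

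The choice of antigen also has content in this trial. The transient and stable CHO proteins are each the immunogen of one arm, so an analysis on only one of them could tilt the comparison toward that arm. The 293F protein is not a plain substitute either: Protocol 4.8 says that 293-produced CH505TF gp120 has a different glycosylation profile from the CHO product.

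**Working it through.** **1. Reproduce the stated power.** Inputs from Protocol 6.1.2: n = 15 per arm, margin 1/4 so log 4 = 1.386, SD 1.2 to 1.6 on the natural log scale, two-sided alpha 0.05, true ratio 1.
- Formula: SE = SD × √(2/15); noncentrality = 1.386/SE; power = P(noncentral t on 28 df > 2.048).
- SD 1.2: SE 0.438, noncentrality 3.164, power 0.863 (stated 0.86).
- SD 1.4: SE 0.511, noncentrality 2.712, power 0.745 (stated 0.74).
- SD 1.6: SE 0.584, noncentrality 2.373, power 0.630 (stated 0.63).

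The protocol's figures are those of one variable tested once.

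**2. Count what the SAP plans at visit 7.** Two readouts (net MFI, AUC) × two populations (all participants, responders) = 4 magnitude comparisons. If each is run on both proteins in the SAP table, 4 × 2 = 8. None is ranked, and none is the non-inferiority test of Protocol 6.1.2.

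**3. Error if either CHO antigen could carry a non-inferiority claim.** Neither document plans this; it measures what the open wording leaves unprevented. Simulation: 15 per arm, SD 1.4, bivariate normal log readouts, true ratio 1/4 on both antigens, the test of step 1 on each, 1,000,000 trials per setting. The documents give no between-antigen correlation, so a range is assumed.

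| Correlation | Either passes | Both pass |
|---|---|---|
| 0.7 | 4.2% | 0.8% |
| 0.8 | 3.9% | 1.0% |
| 0.9 | 3.5% | 1.4% |
| 0.95 | 3.2% | 1.7% |
| 0.99 | 2.8% | 2.2% |

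The nominal one-sided rate is 2.5%.

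**4. One combined variable.** Take each participant's mean of the two log readouts. If each antigen has SD 1.4 and their correlation is ρ, the mean has SD 1.4 × √((1+ρ)/2).
- ρ = 0.8: SD 1.328, SE 0.485, noncentrality 2.858, power 0.79.
- ρ = 0.9: SD 1.365, SE 0.498, noncentrality 2.782, power 0.77.
- ρ = 0.99: SD 1.396, SE 0.510, noncentrality 2.719, power 0.75.

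There is one test, so error stays at 2.5%. The protocol attaches its SD of 1.4 to the log geometric mean FI. If that is already the SD of the combined variable, power is simply 0.74. Requiring both antigens to pass would instead give power of about 0.66 to 0.73 at correlation 0.8 to 0.99.

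**The case against.** The strongest reply is that Protocol 6.1.2 already points to a combination. A geometric mean over the homologous proteins is, on the log scale, the per-participant mean used in step 4, so it cannot be said that the documents have no rule. That is right, and it sets the scope of this point: the SAP drops, and does not clarify, a variable that the protocol indicates ambiguously.

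Three stronger readings are tempting, and the documents do not support them.
- *The better-looking antigen may decide the primary objective.* No passage permits this. The margin appears only in Protocol 6.1.2, attached to one variable, and the SAP's tests are Wilcoxon tests without a margin. The rates in step 3 describe a gap in the wording, not a planned procedure.
- *There are three candidate primary antigens, each tested.* The text offers 293F as an alternative, not an addition, and the table leaves it out. This is a conflict between text and table.
- *Each arm will bind its own protein better, pushing the two antigens in opposite directions.* The documents give no figure for such an effect, and their data suggest that it is small. The amino acid sequences are identical (Protocol 4.3). Dissociation constants were 489.5 and 491.4 nM for UCA, and 9.7 nM for both with CH106 (Protocol 4.4, transient and stable respectively). Mouse sera tested on both proteins gave nearly the same profile, with a slight non-significant trend in favour of the transient immunogen on both (Protocol 4.8.4). Mouse and monoclonal-antibody data do not rule out an effect in human sera, but they give no basis for putting a size on it.

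Identical sequences also make a high between-antigen correlation plausible, which places the error toward the lower end of the range.

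**Conclusion.** The point holds as a failure to carry over and complete the primary variable. Protocol 6.1.2 has one powered variable and one test; SAP 9.3 has several unranked comparisons on other variables, and its text contradicts its own antigen table. This is more than missing detail, because the SAP followed as written does not produce the analysis that the protocol powered.

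The numerical effect of antigen choice alone is modest: about 2.8% to 4.2% one-sided error against 2.5%, and only if either antigen were allowed to carry the claim. That range rests on normal log readouts, SD 1.4, 15 evaluable participants per arm and an assumed correlation of 0.99 to 0.7. A tilt from using one arm's own protein is possible, but the documents do not quantify it. The case for acting rests mainly on having one defined primary answer.

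**What to change.** In SAP 9.3:
1. Reconcile the text with the antigen table, stating whether the 293F protein is assayed and in what role.
2. Define one primary variable: each participant's mean log readout over the transient and stable CHO proteins at visit 7. Name one readout (net MFI at a stated dilution, or AUC), and say how zero or negative values are handled before logs are taken.
3. Test it once as in Protocol 6.1.2, comparing the lower limit of the 95% confidence interval for transient minus stable with log(1/4).
4. Label the two proteins taken separately, the other readout, the responder-only comparisons and any 293F result as supportive, with no separate claims.

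The cost is SAP wording only if both CHO proteins are assayed, as the SAP table states. If the 293F protein had replaced one or both of them, this variable could not be computed without further assays, so the first step comes first. Against the stated 0.74, no power is lost. Parts of SAP 9.3 are written in the past tense. If results by arm have already been seen when the definition is fixed, the report should say so.

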## 5 Objectives and endpoints

### 5.1 Primary objectives and endpoints

*Primary objective 1:*

To evaluate and compare the safety and tolerability of the CH505TF gp120 proteins produced by transient and stable transfection in HIV-1-uninfected, healthy adults

*Primary endpoint 1:*

Local and systemic reactogenicity signs and symptoms, laboratory measures of safety, and AEs and SAEs

*Primary objective 2:*

To evaluate and compare the magnitude of binding antibody responses elicited by the CH505TF gp120 proteins produced via transient and stable transfection methods

*Primary endpoint 2:*

HIV-specific total IgG binding antibody responses against the homologous proteins, as assessed by BAMA at peak timepoint (2 weeks after 3rd vaccination)

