## 6.4.4 Immunogenicity analysis

### 6.4.4.1 General approach

For the statistical analysis of immunogenicity endpoints analyses will be limited to participants who received all scheduled injections per protocol. Assay results that are unreliable, from specimens collected outside of the visit window, or from HIV-infected participants postinfection are excluded. Since the exact date of HIV infection is unknown, any assay data from blood draws 4 weeks prior to an infected participant's last seronegative sample and thereafter may be excluded. If an HIV-infected participant does not have a seronegative sample postenrollment, then all data from that participant may be excluded from the analysis.

Discrete categorical assay endpoints (eg, response rates) will be analyzed by tabulating the frequency of positive response for each assay by antigen and treatment arm at each timepoint for which an assessment is performed. Crude response rates and difference between treatment arms will be presented with their corresponding 95% CI estimates calculated using the score test method (50).

For quantitative assay data, graphical and tabular summaries of the distributions by antigen, treatment arm, and timepoint will be made. For all primary and secondary immunogenicity endpoints, box plots and plots of estimated reverse cumulative distribution curves will be used for graphical display of all of the study arms.

Mean or median (if normality assumption severely violated) assay readouts will be compared between arms and bootstrap CIs will be estimated.

More sophisticated analyses employing repeated measures methodology (for example, linear mixed models or marginal mean models fit by generalized estimating equations) may be utilized to incorporate immune responses over several timepoints and to test for differences over time.

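### The non-inferiority test that Protocol 6.1.2 commits to and sizes for the primary binding-antibody endpoint is carried into neither Protocol 6.4.4 nor SAP 9.3, where the only magnitude tests named are Wilcoxon tests of no difference

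*SAP*

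**What the plan says.** Primary endpoint 2 in Protocol 5.1, repeated in SAP 3.1, is "HIV-specific total IgG binding antibody responses against the homologous proteins, as assessed by BAMA at peak timepoint", two weeks after the third vaccination (visit 7).

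Protocol 6.1.2 gives a hypothesis and a decision rule for it: "We will test the null hypothesis that the geometric mean FI in the transient arm is less than 1/4 of the geometric mean FI", with the stable arm as the reference. It continues, "We will form a 95% confidence interval for the difference in" log_e(FI) between transient and stable, and compares the lower limit with log_e(1/4). The sizing follows from this: "the estimated power to reject the null hypothesis ranges from 0.86 to 0.63 for standard deviation ranging from 1.2 to 1.6". The SD of about 1.4 comes from HVTN 505 data for FI "at the dilutions optimized for immune correlates analyses, which maximize the proportion of samples within the linear range of the dilution-response curve".

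Protocol 6.4, which presents itself as the account of the final analyses, does not repeat the test. Its general text (6.4.4.1, carried over into SAP 9) says: "Mean or median (if normality assumption severely violated) assay readouts will be compared between arms and bootstrap CIs will be estimated".

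For binding-antibody magnitude, SAP 9.3 says that "the Wilcoxon rank sum test was used to compare response magnitudes between treatment groups". The table list in SAP 9.3.1 applies this to net MFI and to AUC, each among all participants and among positive responders. Response rates are compared by Barnard's test. Net MFI is read at 1:50 and truncated at 22,000. AUC is not capped, but it needs a titration, and its dilution series is still an unfilled placeholder.

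**The concern.** Protocol 4.5 gives the goal as showing whether the transient product is as safe and immunogenic as the stable one. That is a non-inferiority question, and the trial was sized for it. The SAP governs the immunogenicity reports, yet it has no margin, no geometric mean ratio, no contrast on log_e FI and no confidence-limit rule. Whoever programs SAP 9.3.1 would deliver p-values against equality and leave the sized question unanswered.

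The SAP also leaves open which comparison carries the primary conclusion. With the two antigens in its table there are up to 4 Wilcoxon magnitude tests at visit 7 (2 antigens × all participants or responders) on net MFI, and up to 8 if titration adds AUC.

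**Working it through.** **Inputs.** From Protocol 6.1.2: n = 15 per arm, margin 1/4, SD 1.2, 1.4 and 1.6, two-sided alpha 0.05, log_e FI normal with equal spread. Assumed: a true ratio of 1 for the power figures, which the protocol does not state but which reproduces its table; and two-sided 0.05 for Wilcoxon, since the SAP gives no level.

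**Step 1: reproduce the stated power.** SE = SD × √(2/15). Noncentrality = log_e(4)/SE, with log_e(4) = 1.386. Power = P(noncentral t with 28 df > 2.048).

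| SD | SE | Noncentrality | Power | Stated |
|---|---|---|---|---|
| 1.2 | 0.438 | 3.16 | 0.863 | 0.86 |
| 1.4 | 0.511 | 2.71 | 0.745 | 0.74 |
| 1.6 | 0.584 | 2.37 | 0.630 | 0.63 |

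All 27 cells of Table 6-3 agree within 0.01. A normal approximation gives 0.886, 0.774 and 0.660, and a one-sided 0.05 level gives 0.925, 0.841 and 0.749; neither fits. The table is therefore the power of a t-based non-inferiority test at one-sided 0.025.

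**Step 2: what each method asks of the data.** The 95% CI half-width on the log scale is 2.048 × SE = 0.898, 1.047, 1.197, or 2.45-, 2.85- and 3.31-fold. Non-inferiority needs an observed ratio above 0.25 × fold = 0.61, 0.71, 0.83. A t-test of no difference stays non-significant down to 1/fold = 0.41, 0.35, 0.30. Observed ratios between those limits are non-significant without showing non-inferiority.

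**Step 3: behaviour at the margin.** Simulated trials with normal log_e FI, 15 per arm and a true ratio of 1/4:

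| SD | Wilcoxon non-significant | Protocol rule declares non-inferiority |
|---|---|---|
| 1.2 | 17% | 2.5% |
| 1.4 | 29% | about 2.5% |
| 1.6 | 41% | 2.5% |

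**Step 4: other true ratios, for context.** Wilcoxon is non-significant while non-inferiority is not shown in about 12%, 23% and 35% of trials at a true ratio of 1, and in 37%, 51% and 61% at 1/2. These are mostly type II error of the non-inferiority test itself: 1 − power at ratio 1 is 14%, 26% and 37%. Adding the test would not recover those trials. Conversely, with equal products about 2% of trials have a significant Wilcoxon although non-inferiority is shown.

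**Step 5: do the SAP's inputs match the test?**
- Readout: the SD of 1.4 is for FI in the linear range. SAP net MFI at 1:50 is capped at 22,000, and capping in both arms pulls them together; the documents do not allow the amount to be estimated. AUC is a different quantity from the FI of Protocol 6.1.2.
- Antigen: Protocol 6.1.2 speaks of homologous proteins and then of a panel of Envs. SAP 9.3 plans dilutions "for a total of six dilution points if titrations are warranted against CH505TF gp120 (transient transfection) and CH505TF gp120 (stable transfection) or" a 293F protein, but its table lists only the transient and stable gp120.

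**Step 6: evaluable numbers.** The analysis is per-protocol and the sizing makes no allowance for losses. At SD 1.4, power is 0.71 with 14 per arm, 0.68 with 13 and 0.64 with 12.

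**The case against.** The best defence is that nothing has been withdrawn. The commitments in Protocol 6.1.2 stand, and the bootstrap interval in SAP 9 could be set against the 1/4 margin by anyone who knew of it. This is right as far as it goes. But that sentence allows means or medians, names no log scale, margin or rule, and has no table in SAP 9.3.1.

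A second defence is that the SAP merely follows Protocol 6.4.4.1, which also lacks the test, and that objective 2 says only evaluate and compare. This stands too. The gap is shared, and correcting SAP 9.3 alone would leave the two protocol sections unreconciled.

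Several stronger readings are tempting but unsupported:
- That the SAP takes a non-significant Wilcoxon as proof of non-inferiority. It does not say so; the rates in Step 3 show why the substitution would fail, not that it was planned.
- That the rates in Step 4 measure harm from the omission. They mostly reflect limited power.
- That the analysis population is open. Protocol 6.4 and SAP 4 and 9 fix it as per-protocol. What is missing is a statement that all participants, not responders only, carry the primary test.
- That the antigen is wholly undefined. The two gp120 proteins in the SAP table are the natural meaning of homologous; only the 293F alternative and the manner of combining are loose.
- That choices were made after unblinded data were seen. SAP 9.3 is in the past tense and its approval e-mail is dated August 2023, but the documents do not settle this.

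**Conclusion.** The point holds as an omission shared by Protocol 6.4.4 and SAP 9.3, and it should be corrected because it concerns the one test that the sample size supports for a primary endpoint. The stated power is correct for the test in Protocol 6.1.2 and does not describe any test named in SAP 9.3.

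The relevant size is the contrast at the margin: about 17%, 29% and 41% non-significant Wilcoxon results, against about 2.5% false non-inferiority under the protocol rule. It rests on normal log_e FI with equal SDs of 1.2 to 1.6, 15 evaluable per arm and a two-sided 0.05 Wilcoxon. The existence of the gap depends on none of these. The stated power carries over only with 15 evaluable per arm and if the assumed SD holds for the readout chosen.

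**What to change.** 1. In SAP 9.3 and 9.3.1, with a matching sentence in Protocol 6.4.4, add the Protocol 6.1.2 test as the primary analysis of endpoint 2: visit 7, per-protocol set, all participants regardless of response. Report the geometric mean ratio (transient/stable) with its two-sided 95% CI, and conclude non-inferiority if the lower limit exceeds 1/4.
2. State the interval method. A t-based interval on log_e FI matches the power calculation. If the bootstrap is used, name its type: a percentile bootstrap, simulated under the same assumptions, gave false non-inferiority of about 3.5%.
3. State the readout and dilution, preferring one in the linear range if titration was done. If 1:50 is used, report the number of values at the ceiling by arm and note that capping pulls the arms together.
4. State whether the two homologous gp120 proteins are tested separately or as a geometric mean within participant (a possible reading of Protocol 6.1.2), and resolve the 293F alternative.
5. Label the Wilcoxon, Barnard and responder-only comparisons as supportive.
6. If readout or antigen choices are made after unblinded assay data were seen, disclose it. Margin, scale and rule were already fixed in protocol version 1.0 (December 2018).

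Cost: wording in two documents and one table. Sample size, visits and assays do not change.
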